**Description :**

The purpose of this reporting and analysis plan (RAP) is to:

- Describe the safety, tolerability, and pharmacokinetics analyses required for the study which will be provided to the study team members to convey the content of the reporting efforts, specifically Statistical Analysis Complete (SAC).

## 1. REPORTING & ANALYSIS PLAN SYNOPSIS

Overview	Key Elements of the Reporting and Analysis Plan
Purpose	
The purpose of this reporting and analysis plan (RAP) is to describe:
 
 
Planned analyses and output for the study.
 

Protocol	
 
Reporting and Analysis Plan is based on original protocol (Dated: 04-APR-2017) for study GSK2269557/207674 [GlaxoSmithKline Document Number: 2017N316562_00].
 

Primary Objective / Endpoint	
 
Primary objective is to assess the pharmacokinetic profile of a single dose of GSK2269557 administered via the ELLIPTA™ dry powder inhaler to healthy participants by derived pharmacokinetic parameters including: Area under the plasma drug concentration versus time curve from zero to time t AUC(0-t), Area under the plasma drug concentration versus time curve from zero to 24 hours AUC(0-24), Area under the plasma drug concentration versus time curve from zero to infinity AUC(0-<math>\inf\infty</math>), Maximum observed plasma drug concentration (Cmax), Time to maximum observed plasma drug concentration (Tmax), Concentration at trough (Ctrough), Terminal half-life (T1/2), where data allow.
 

Study Design	
 
Randomised, double-blind, parallel group, single dose study in healthy participants.
 
Approximately 12 participants will be randomised to receive a single dose of GSK2269557 750 µg or a single dose of GSK2269557 500 µg in a 1:1 ratio.
 

Analysis Population	
 
Primary: Pharmacokinetic Population (Comprised of All randomised participants who take at least 1 dose of study treatment and for whom a pharmacokinetic sample was obtained and analysed. Participants will be analysed according to the treatment they received).
 

Hypothesis	
 
There are no formal hypotheses being tested in the study; instead an estimation and inference approach will be adopted to evaluate the objectives.
 

Primary Analyses	
 
Pharmacokinetic data will be presented in tabular and/or graphical format and summarized descriptively according to GSK's Integrated Data Standards Library (IDSL) standards. Individual GSK2269557 plasma concentration-time profiles (by treatment and subject) and median/mean (<math>\pm</math>SD) profiles by treatment group will be plotted and listed. Plasma concentration time data for GSK2269557 will be analyzed by non-compartmental methods using WinNonlin and derived PK parameters summarised and listed. No formal statistical analyses will be conducted.
 

Secondary Analyses	
 
Safety data will be presented in tabular format and summarized descriptively.
 

## 2. SUMMARY OF KEY PROTOCOL INFORMATION

### 2.1. Changes to the Protocol Defined Statistical Analysis Plan

There were no changes or deviations to the originally planned statistical analysis specified in the protocol [Dated: 04-APR-2017].

### 2.2. Study Objective(s) and Endpoint(s)

Objectives	Endpoints
Primary (Pharmacokinetic)	Primary (Pharmacokinetic)

 
To assess the pharmacokinetic profile of a single dose of GSK2269557 administered via the ELLIPTA dry powder inhaler to healthy participants.
 
	
 
GSK2269557 plasma concentration data and derived pharmacokinetic parameters including area under the plasma drug concentration versus time curve from zero to time t (AUC(0-t)), area under the plasma drug concentration versus time curve from zero to 24 hours (AUC(0-24)), area under the plasma drug concentration versus time curve from zero to infinity (AUC(0-inf<math>\infty</math>)), maximum observed plasma drug concentration (Cmax), time to maximum observed plasma drug concentration (Tmax), Concentration at trough (Ctrough), terminal half-life (T1/2), where data allow.
 

Secondary Objectives (Safety)	Secondary Endpoints (Safety)

 
To assess the safety and tolerability of a single dose of GSK2269557 administered via the ELLIPTA dry powder inhaler to healthy participants.
 
	
 
Safety and tolerability of GSK2269557 as assessed by clinical monitoring of: 
 
Vital Signs
 
Electrocardiogram (ECG)
 
Spirometry
 
Laboratory safety data
 
Adverse events (AEs)
 
 
 

## 2.3. Study Design

Overview of Study Design and Key Features	
Design Features	
 
Randomised, double-blind, parallel group single centre study to investigate the safety, tolerability, and pharmacokinetics of a single dose of GSK2269557 administered via the ELLIPTAT dry powder inhaler to healthy participants.
 

Dosing	
 
Patients dosed within 28 days of screening.
 
Study treatment will be administrated on Day 1. Participants will be discharged after completion of all 24h post dose assessments on Day 2 and if there are no safety concerns
 

Treatment Assignment	
 
Approximately 12 participants will be randomised to receive a single dose of GSK2269557 750 µg or a single dose of GSK2269557 500 µg in a 1:1 ratio.
 

## 2.4. Statistical Hypotheses

There are no formal hypotheses being tested in the study; instead an estimation and inference approach will be adopted to evaluate the objectives.

## 3. PLANNED ANALYSES

### 3.1. Final Analyses

The final planned primary analyses will be performed after the completion of the following sequential steps:

- [1] All subjects have completed the study as defined in the protocol.
- [2] All required database cleaning activities have been completed and final database release and database freeze has been declared by Data Management.
- [3] All criteria for unblinding the randomisation codes have been met.
- [4] Randomisation codes have been distributed according to RandAll NG procedures.

## 4. ANALYSIS POPULATIONS

Population	Definition / Criteria	Endpoint(s) Evaluated
All Participants Enrolled (APE) Population	
 
All participants for whom a record exists on the study database; includes both screen participants and participants who are not screened but sign the informed consent form
 
	
 
Study Population
 

Safety	
 
All randomised participants who receive at least one dose of study treatment. Participants will be analysed according to the treatment they actually received.
 
	
 
Study Population
 
Safety
 

Population	Definition / Criteria	Endpoint(s) Evaluated
Pharmacokinetic	
 
• All randomised participants in the Safety population and for whom a pharmacokinetic sample was obtained and analysed.
 
	
 
• PK
 

**NOTES :**

- Please refer to [Appendix 7](#) which details the population to be used for each display being generated.

#### 4.1. Protocol Deviations

- Important protocol deviations (including deviations related to study inclusion/exclusion criteria, conduct of the trial, patient management or patient assessment) will be summarised and listed.
- Protocol deviations will be tracked by the study team throughout the conduct of the study in accordance with the Protocol Deviation Management Plan.
  - Data will be reviewed prior to unblinding and freezing the database to ensure all important deviations are captured and categorised on the protocol deviations dataset.
  - This dataset will be the basis for the summaries and listings of protocol deviations.
- A separate summary and listing of all inclusion/exclusion criteria deviations will also be provided. This summary will be based on data as recorded on the inclusion/exclusion page of the eCRF.

### 5. CONSIDERATIONS FOR DATA ANALYSES AND DATA HANDLING CONVENTIONS

[Table 1](#) provides an overview of appendices within the RAP for outlining general considerations for data analyses and data handling conventions.

**Table 1      Overview of Appendices**

Section	Component
10.1	Appendix 1: Time & Events
10.2	Appendix 2: Treatment States and Phases
10.3	Appendix 3: Data Display Standards & Handling Conventions
10.4	Appendix 4: Derived and Transformed Data
10.5	Appendix 5: Premature Withdrawals & Handling of Missing Data
10.6	Appendix 6: Values of Potential Clinical Importance

## 6. STUDY POPULATION ANALYSES

### 6.1. Overview of Planned Analyses

The study population analyses will be based on the “Safety” or “APE” population, unless otherwise specified.

**Table 2** provides an overview of the planned study population analyses, with full details of data displays being presented in [Appendix 8: List of Data Displays](#).

**Table 2 Overview of Planned Study Population Analyses**

Display Type	Data Display's Generated		
	Figure	Table	Listing
Randomisation			
Randomisation			Y
Subject Disposition			
Subject Disposition		Y	
Reasons for Screening Failures		Y	Y
Reasons for Withdrawals			Y
Important Protocol Deviations		Y	Y
Inclusion and Exclusion Criteria Deviations			Y
Demography			
Demographics Characteristics		Y	Y
Age Ranges		Y	
Race & Racial Combinations		Y	Y
Study Populations		Y	
Medical Condition & Concomitant Medications			
Medical Conditions (Current/Past)			Y
Concomitant Medication			Y

**NOTES:**

- Y = Yes display generated.

## 7. PRIMARY STATISTICAL ANALYSES

### 7.1. Pharmacokinetic Analyses

The primary pharmacokinetic analyses will be based on the “Pharmacokinetic” population, unless otherwise specified.

#### 7.1.1. Overview of Planned Pharmacokinetic Analyses

[Table 3](#) provides an overview of the planned pharmacokinetic analyses with full details of data displays being presented in [Appendix 8](#): List of Data Displays.

**Table 3 Overview of Planned Pharmacokinetic Analyses**

Endpoints	Untransformed				Log-Transformed			
	Summary		Individual		Summary		Individual	
	F	T	F	L	F	T	F	L
Plasma Concentrations	Y	Y	Y	Y	Y	Y	Y	
Derived PK Parameters		Y		Y		Y		

**NOTES :**

- T = Table, F = Figures, L = Listings, Y = Yes display generated.
- Summary = Represents TFL related to any summaries (descriptive statistics) of the observed raw data.
- Individual = Represents FL related to any displays of individual subject observed raw data.

#### 7.1.2. Drug Concentration Measures

Refer to [Appendix 4](#): Data Display Standards & Handling Conventions (Section [10.3.3](#) Reporting Process & Standards).

#### 7.1.3. Pharmacokinetic Parameters

##### 7.1.3.1. Deriving Pharmacokinetic Parameters

- Refer to [Appendix 4](#): Data Display Standards & Handling Conventions (Section [10.3.3](#) Reporting Process & Standards).
- The pharmacokinetic parameters will be calculated by standard non-compartmental analysis according to current working practices and using Win Nonlin Pro.
- All calculations of non-compartmental parameters will be based on actual sampling times recorded during the study.
- Pharmacokinetic parameters described in [Table 4](#) will be determined from plasma GSK2269557 concentration-time data, as data permits.

**Table 4** **Derived Pharmacokinetic Parameters**

Parameter	Parameter Description
AUC(0-t)	Area under the concentration-time curve from time zero to the time of the last quantifiable concentration (C(t)) will be calculated using the linear trapezoidal rule for each incremental trapezoid and the log trapezoidal rule for each decremental trapezoid.
AUC(0-24)	
Area under the concentration-time curve will be calculated to fixed nominal time 24 hours after administration (AUC(0-24)), using the combination of linear and logarithmic trapezoidal methods (i.e., Linear Up/Log Down calculation method in Phoenix WinNonlin Professional).
 
If a sampling time deviation occurred at nominal time 24 hours after administration (and 24 < t), AUC(0-24) will be calculated using the concentration at time 24 hours after administration post-dose estimated by the method of interpolation.
 
If nominal time 24 hours after administration > t (or if the concentration at time 24 hours after administration was below then limit of quantification), then the concentration (y) at time 24 hours after administration is estimated using lambda_z and last observed Ct according to the formula:
 $y = Ct(\text{obser}) \times e^{-\lambda z(24-t)}$ 
Then the following equation will be used to calculate (AUC(0-24)) where t is the time of last quantifiable plasma concentration.
 $\text{AUC}(0-24) = \text{AUC}(0-t) + \text{AUC}(t-24)$ 
If lambda_z is not estimable, a partial AUC is not calculated (when 24 > t).

AUC(0- $\text{inf}^\infty$ )	
Area under the concentration-time curve from zero time (pre-dose) extrapolated to infinite time (AUC(0-inf)) will be calculated as follows:
 $\text{AUC}(0-\text{inf}) = \text{AUC}(0-t) + Ct / \lambda z.$
Cmax	Maximum observed concentration, determined directly from the concentration-time data.
tmax	Time to reach Cmax, determined directly from the concentration-time data.
Ctrough	Trough observed concentration, will be obtained directly from the concentration-time data.
t 1/2	
Apparent terminal half-life will be calculated as:
 $t_{1/2} = \ln 2 / \lambda z$ 
(NOTE: <math>\lambda z</math> is the terminal phase rate constant).

**NOTES:**

- Additional parameters may be included as required.

### 7.1.3.2. Statistical Analysis of Pharmacokinetic Parameters

There are no planned statistical analyses.

## 8. SECONDARY STATISTICAL ANALYSES

### 8.1. Safety Analyses

#### 8.1.1. Overview of Planned Safety Analyses

The safety analyses will be based on the “Safety” population, unless otherwise specified.

[Table 5](#) provides an overview of the planned analyses, with full details being presented in [Appendix 8: List of Data Displays](#).

**Table 5 Overview of Planned Safety Analyses**

Endpoint	Absolute				Change from Baseline			
	Summary		Individual		Summary		Individual	
	T	F	F	L	T	F	F	L
Adverse Events								
All AE's	Y				Y			
All Drug-Related AE's	Y							
Serious AE's	Y				Y			
Non Serious AE's	Y							
Withdrawal AE's	Y				Y			
Laboratory Values								
Clinical Chemistry					Y			
Hematology					Y			
Urinalysis	Y							
ECG's								
ECG Findings	Y							
ECG Values	Y				Y			
Vital Signs								
Vitals Values					Y			
Emergent Vital Signs					Y	Y		
Spirometry								
FEV1	Y				Y	Y		
FVC	Y				Y	Y		

**NOTES :**

- T = Table, F = Figures, L = Listings, Y = Yes display generated.
- Summary = Represents TFL related to any summaries (i.e. descriptive statistics) of the observed raw data.
- Individual = Represents FL related to any displays of individual subject observed raw data.

#### **8.1.1.1. Statistical Analysis of Safety Parameters**

There are no planned statistical analyses.

## 10. APPENDICES

Section	Appendix
RAP Section 5 : General Considerations for Data Analyses & Data Handling Conventions	
Section 10.1	Appendix 1 : Time and Events
Section 10.2	Appendix 2 : Treatment States & Phases
Section 10.3	Appendix 3 : Data Display Standards & Handling Conventions 
 
• Study Treatment & Sub-group Display Descriptors
 
• Baseline Definitions & Derivations
 
• Reporting Process & Standards
 

Section 10.4	Appendix 4 : Derived and Transformed Data 
 
• General
 
• Study Population
 
• Safety
 

Section 10.5	Appendix 5 : Premature Withdrawals & Handling of Missing Data
Section 10.6	Appendix 6 : Values of Potential Clinical Importance 
 
• Laboratory Values
 
• ECG
 
• Vital Signs
 

Other RAP Appendices	
Section 10.7	Appendix 7 : Abbreviations & Trade Marks
Section 10.8	Appendix 8 : List of Data Displays

## 10.1. Appendix 1: Time & Events

### 10.1.1. Protocol Defined Time & Events

Procedure	Screening (up to 28 days before Day 1)	Treatment Period [Days]					Follow-up (10-12 days post dose)	Notes
		-1	1	2	3	6		
Informed consent	X							
Inclusion and exclusion criteria	X							Recheck clinical status before randomization
Demography	X							
Full physical examination including height and weight	X							
Medical history (includes substance usage and current medical conditions)	X							Substances: Drugs, Alcohol, tobacco and caffeine
Urine pregnancy test (WOCBP only)	X	X						

Procedure	Screening (up to 28 days before Day 1)	Treatment Period [Days]					Follow-up (10-12 days post dose)	Notes
		-1	1	2	3	6		
HIV, Hepatitis B and C screening	X							If test otherwise performed within 3 months prior to first dose of study treatment, testing at screening is not required
Admission to unit		X						
Outpatient visit					X	X		
Discharge				X				
Laboratory assessments (include liver chemistries)	X	X		X				
Urine Drug, Alcohol and Smoking breath test	X	X						

Procedure	Screening (up to 28 days before Day 1)	Treatment Period [Days]					Follow-up (10-12 days post dose)	Notes
		-1	1	2	3	6		
12-lead ECG	X		X	X				Screening only: ECG in triplicate Day 1: pre-dose, 5 mins & 6 hrs post- dose Day 2: before discharge
Vital signs	X		X	X				Screening only: VS in triplicate Day 1: pre-dose, 1h and 6h post-dose
FEV1 and FVC (triplicate)	X		X					Day 1: pre-dose, 30 min post-dose
Brief physical examination		X						

Procedure	Screening (up to 28 days before Day 1)	Treatment Period [Days]					Follow-up (10-12 days post dose)	Notes
		-1	1	2	3	6		
Inhaler training		X						Training conducted by reviewing the Patient Information Leaflet with the participant. Additional training may be conducted at the discretion of the investigator.
Dosing study treatment			X					
AE review			←=====→					
SAE review			←=====→					
Concomitant medication review			X	X	X	X	X	
Pharmacokinetic blood sample			X	X	X	X		Day 1: pre-dose, 5 min and 0.5, 2, 6 and 12 hours post-dose. Day 2: 24 hours post-dose. Day 3: 48 hours post-dose Day 6: 120 hours post dose.

- The timing and number of planned study assessments, including safety and pharmacokinetic assessments may be altered during the course of the study based on newly available data (e.g., for safety purposes or to obtain data closer to the time of peak plasma concentrations) to ensure appropriate monitoring.
- Any changes in the timing or addition of time points for any planned study assessments must be documented and approved by the relevant study team member and then archived in the sponsor and site study files, but will not constitute a protocol amendment. The IRB/IEC will be informed of any safety issues that require alteration of the safety monitoring scheme or amendment of the ICF

## 10.2. Appendix 2: Treatment States and Phases

### 10.2.1. Treatment Phases

Assessments and events will be classified according to the time of occurrence relative to dosing.

Treatment Phase	Definition
Pre-Treatment	Date $\leq$ Study Treatment Start Date
On-Treatment	Study Treatment Start date $<$ Date $\leq$ Study Treatment Stop Date
Post-Treatment	Date $>$ Study Treatment Stop Date

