### 10.2.2. Treatment States

Assessments and events will be classified according to time of occurrence relative to the start and/or stop date of the study treatment.

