#### 10.2.2.1. Treatment States for AE Data

Treatment State	Definition
Pre-Treatment	AE Start Date $<$ Study Treatment Start Date
On-Treatment	If AE onset date is on or after treatment start date & on or before the treatment stop date Study Treatment Start Date $\leq$ AE Start Date $\leq$ Study Treatment Stop Date [+ 1]
Post-Treatment	If AE onset date is after the treatment stop date AE Start Date $>$ Study Treatment Stop Date
Onset Time	If Treatment Start Date $>$ AE Onset Date = AE Onset Date - Treatment Start Date
Since First Dose (Days)	If Treatment Start Date $\leq$ AE Onset Date = AE Onset Date - Treatment Start Date + 1 Missing otherwise
Duration (Days)	AE Resolution Date – AE Onset Date + 1
Drug-related	If relationship is marked 'YES' on eCRF OR value is missing

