### 10.4.2. Study Population

Demographics
Age

 
GSK standard algorithms will be used for calculating age where birth date is imputed as: 
 
Any subject with a missing day will have this imputed as day ‘15’.
 
Any subject with a missing date and month will have this imputed as ‘30th June’.
 
 
 
Birth date will be presented in listings as ‘YYYY’.
 

Body Mass Index (BMI)

 
Calculated as <math>\text{Weight (kg)} / [\text{Height (m)}]^2</math>
 

Extent of Exposure

 
Number of days of exposure to study drug will be calculated based on the formula:  Duration of Exposure in Days = Treatment Stop Date – (Treatment Start Date) + 1 
 
Subjects who were randomized but did not report a treatment start date will be categorised as having zero days of exposure.
 

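### SAP date rules do not suit a single dose: a missing AE stop day can give a zero or negative duration and the On-Treatment phase is empty; separately, the AE On- and Post-Treatment states overlap (minor)

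*SAP*

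**What the plan says.** **Dosing.** SAP 2.3 places the single dose on one day: "Study treatment will be administrated on Day 1". The SAP never states a treatment stop date, but its exposure formula in 10.4.2 needs one: "Duration of Exposure in Days = Treatment Stop Date – (Treatment Start Date) + 1".

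**Phases (SAP 10.2.1).** The stated aim is that "Assessments and events will be classified according to the time of occurrence relative to dosing". Pre-Treatment is "Date $\leq$ Study Treatment Start Date", On-Treatment is "Study Treatment Start date $<$ Date $\leq$ Study Treatment Stop Date", and Post-Treatment is any date after the stop date.

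**AE states (SAP 10.2.2 and 10.2.2.1).** The introduction reads "Assessments and events will be classified according to time of occurrence relative to the start and/or stop date of the study treatment", but the table that follows defines states for AEs only. In words, AE On-Treatment ends at the stop date. The formula beside the words is "Study Treatment Start Date $\leq$ AE Start Date $\leq$ Study Treatment Stop Date [+ 1]", which runs one day longer. Post-Treatment is onset after the stop date. AE duration is resolution date minus onset date plus 1. A note adds that if the treatment stop date is missing, the AE counts as On-Treatment.

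**Missing AE stop day (SAP 10.5.2.1).** For calculating onset time and duration, a missing stop day becomes month-end. If month-end is later than the treatment stop date, the treatment stop date is used instead.

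**Partial AE dates (SAP 10.5.2.2).** These go first to data management. If still unresolved, a partial stop date takes the last day of the month, with 'Dec' for the month and no cap at treatment stop.

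**The concern.** A cap at treatment stop, and a phase that opens strictly after the start date, make sense only when treatment lasts more than a day. Here AEs are collected from dosing until the follow-up contact 10–12 days later (Protocol 9.1.1 and Synopsis), so most of the collection period lies after the date to which the cap pulls an AE's end. An AE can then be recorded as ending before it began.

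The same collapse empties the On-Treatment phase and leaves the label of Day 1 post-dose assessments dependent on how the rule is read. For example, spirometry is scheduled at "Day 1: pre-dose, 30 min post-dose", so one calendar date holds both a baseline and a post-dose value.

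The overlap in AE states is a separate fault and would exist with any number of doses.

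At stake is whether AE duration, AE state and phase, as the SAP defines them, can be derived sensibly and in the same way by two programmers.

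**Working it through.** The plan states no figure on this point, so there is none to reproduce. The rules were applied literally.

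**Inputs**
- One dose on Day 1 (SAP 2.3). Start = stop = Day 1 is inferred. The exposure formula then gives 1 − 1 + 1 = 1 day, which is sensible.
- AE duration = resolution − onset + 1 (SAP 10.2.2.1).
- Last planned contact is 10–12 days post dose, which is Day 11 to Day 13 (Protocol Synopsis).
- Assessment times come from SAP 10.1.1.

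**1. Missing stop day under 10.5.2.1.** Take onset on Day d with d > 1. The end of the stop month cannot be earlier than onset, so it is later than Day 1. The cap therefore always applies and the imputed end is Day 1:

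duration = 1 − d + 1 = 2 − d

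| Onset day | Derived duration (days) |
|---|---|
| 1 | 1, whatever the true length |
| 2 | 0 |
| 3 | −1 |
| 6 | −4 |
| 11 | −9 |
| 13 | −11 |

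This was checked for every dosing date in 2016–2018, with onset on Days 1–13 and true resolution from onset to Day 13. With onset after Day 1 there were 85,488 combinations; the cap applied in all of them and none gave a positive duration. Taking the end of the known month without the cap gave a minimum of 1 day.

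Assumed example: dose 10 May, onset 13 May, stop recorded only as May.
- 10.5.2.1: 10 − 13 + 1 = −2 days.
- 10.5.2.2, keeping the recorded month: 31 − 13 + 1 = 19 days.
- Month-end limited to a last contact on 20–22 May: 20 − 13 + 1 = 8 to 22 − 13 + 1 = 10 days.

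If the start day is missing too, and the first of the onset month falls before dosing, onset is set to Day 1 and the duration is 1 day.

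**2. Phases under 10.2.1.** The condition 1 < date ≤ 1 has no solution, so On-Treatment is empty. There are eight scheduled post-dose safety time points: three ECG, three vital signs, one spirometry and one laboratory.
- By calendar date, the five on Day 1 (ECG at 5 min and 6 h, vital signs at 1 h and 6 h, spirometry at 30 min) are Pre-Treatment and the three on Day 2 are Post-Treatment.
- By date and time, all eight are Post-Treatment.

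On-Treatment is empty either way. Section 10.2.1 also covers events: by calendar date a Day 1 AE is Pre-Treatment there but On-Treatment in 10.2.2.1.

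**3. AE states under 10.2.2.1, Day 2 onset.**
- Words: 2 > 1, so Post-Treatment only.
- Formula: 1 ≤ 2 ≤ 1 + 1, so On-Treatment; and 2 > 1, so Post-Treatment as well.

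For any stop date, an onset one day later meets both definitions if the bracketed term applies.

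**Sensitivity to the inferred stop date.**
- Recorded as Day 2: the 10.2.1 On-Treatment phase holds Day 2 only, and the capped duration is 2 − d + 1 = 3 − d, which is zero or negative from a Day 3 onset.
- Left blank: the note in 10.2.2.1 makes every AE On-Treatment, and the cap has no date to act on.

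**The case against.** The strongest reply is that no planned result is shown to change. PK parameters use actual sampling times (SAP 7.1.3.1), baseline is the latest pre-dose assessment (10.3.2.1), change from baseline follows from it, and summaries use planned time relative to dosing (10.3.3). No Appendix 8 title is split by phase or state or names AE duration, and the display shells are not in the documents. This stands, and it is why the point is minor.

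Other parts of the reply also stand. The stop date is inferred. A date-and-time reading of 10.2.1 gives, in effect, a pre-dose/post-dose split. The bracketed '[+ 1]' may be a template remnant. A negative duration needs an AE with onset after Day 1, a missing stop day that survives the data management query, and 10.5.2.1 rather than 10.5.2.2 as the rule programmed. With about 12 participants that may be rare.

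Three stronger readings are tempting but not supported:
- A reader might infer that every AE starting after Day 1 gets an impossible duration. AEs with full dates are unaffected.
- A reader might infer that 5 × 12 = 60 of 8 × 12 = 96 post-dose participant-time points are mislabelled Pre-Treatment. That count needs the calendar-date reading, and no output is shown to use the label.
- A reader might take 10.5.2.2 to turn the May example into 31 December, a duration of 233 days. That applies 'Dec' over a recorded month, although the rule makes the day depend on the month and year.

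The reply does not rescue the text. The SAP has two incompatible stop-date rules, one of which can end an event before it starts, and it defines a phase that can hold nothing.

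**Conclusion.** Wrong as written, and minor. Assuming start = stop = Day 1:
- the 10.5.2.1 cap gives 2 − d days for a missing stop day with onset on Day d after Day 1, from 0 down to −11 at Day 13, and conflicts with 10.5.2.2;
- the 10.2.1 On-Treatment phase is empty, and the phase of Day 1 post-dose assessments depends on whether date or date and time is used.

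The double state in 10.2.2.1 does not depend on single dosing. It rests only on whether '[+ 1]' is meant to apply, and it affects one onset day, Day 2 here.

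A reader might go on to infer that AE counts or the safety conclusions are at risk. The documents show no effect on AE totals, on the primary PK endpoint or on any planned summary. The fault is confined to derived phase, state and duration values.

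**What to change.** - **10.5.2.1 and 10.5.2.2:** delete the cap at treatment stop and use one AE stop-date rule in both places. Impute the last day of the known month, and use 'Dec' only when the month is missing. Limit the result to the participant's last recorded study contact, and never let it precede onset.
- **10.2.1:** replace the three phases with pre-dose and post-dose, assigned by time relative to dosing.
- **10.2.2.1:** delete '[+ 1]' so that On- and Post-Treatment do not overlap. Alternatively, use one treatment-emergent state: onset on or after dosing, including related SAEs reported after the follow-up contact, which Protocol 9.1.1 requires to be notified.

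The cost is SAP wording and one derivation. Planned time relative to dosing is already used for summaries (SAP 10.3.3), and no assessment, visit or dose changes.
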